7.1 Study Subjects

7.1.1 Disposition of Subjects

Disposition of subjects will be reported following the STROBE Statement Checklist. Number of individuals at each stage of study (number of total assessed for eligibility, number enrolled, number analyzed and number with 1 month follow-up) will be reported. Reason for not participation at each stage will be reported where known.

Table 1 - Number of Subject Screened and Enrollments by Site and Ward

Figure 1 – Subject Enrollment Accrual by Site and Ward Ove Time

Figure 2 – Flow diagram of Patient Disposition

[figure not shown]

Table 2 - Screening for Eligibility by Inclusion Criteria- FAS

Table 3 - Screening for Eligibility by Exclusion Criteria- FAS

7.1.2 Clinical Investigation Plan (CIP) Deviations

All deviations will be collected in the case report form, with the type of the deviation and the reason for the deviation. All Deviations will be reviewed and classified by the clinical study team. The following tables will describe study deviations:

Table 4 - Protocol Deviation by Reason - FAS

Table 5 - Protocol Deviation by Visit - FAS

Listing 1a. Other deviations - FAS

Protocol deviation will be defined as major protocol deviation if the deviation impacts on the primary objective, such as:

- Enrolled subject did not meet enrolment criteria or eligibility criteria not met (i.e. subject didn't undergo opioid therapy or patient not transferred to the ward).

The following listing will be produced:

Listing 1b. Major Protocol deviations - FAS

7.1.3 Analysis Sets

The following subject sets will be used for the analysis:

- The Full Analysis Set (FAS) includes all patients enrolled in the study those sign Patient Informed Consent, fulfill the inclusion and exclusion criteria. The FAS will be used for safety evaluation.
- The Modified Full Analysis Set (MFAS) includes all patients enrolled in the study those sign Patient Informed Consent, fulfill the inclusion and exclusion criteria, start opioid therapy and monitored in the ward. Patients will not be excluded from the MFAS population even if prematurely stops, intermittent use or does not start the monitoring. Patients with major protocol deviations will be excluded from the MFAS. The MFAS will be used to evaluate the primary analysis.
- The Potential Respiratory Depression Population Set (PRDPS) includes all patients in the MFAS and have at least one Episode-File and/or Clinical Event to be adjudicated. The PRDPS will be used for secondary endpoint#2.

The following table shows how each population set will be used for analyses:

Population set	Baseline assessment	Primary and Secondary Endpoints (#1,#3)	Secondary Endpoint#2	Adverse Events
FAS	√			√
MFAS	√	√		√
PRDPS	√		√	

For those patients who have less than the minimum monitoring, or who drop out of the study, the analyses will include all data up to the point of their last data collection.

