9.10. Recording Data

The investigator will clearly mark the clinical records to indicate that the subject is enrolled in this clinical study. Subject's medical record will be used as source documents. Worksheets could serve as source documentation in particular cases if a data field is not in the subject's medical record.

Capnostream device memory data will be the source for the number and duration of RD episodes. RD data reports will be derived from the device memory data. The reports are used for primary endpoint validation from the Clinical Event Committee.

The investigator must ensure accuracy, completeness and timeliness of the data reported in the eCRFs and in all other required reports. Data reported on the eCRFs which are derived from source documents, such as patient medical records, must be consistent with the source documents or the discrepancies need to be justified in a documented rationale, signed and dated by the (principal) investigator, to be filed in the subject file. All baseline and medical history data must be derived from source documents.

Only authorized persons can complete eCRFs. Training will be provided to site personnel on the use of data collection tools. CRFs shall be electronically signed by investigators (physician) or by authorized site staff as specified on the Delegated Tasks List. Final version of eCRFs will be provided to the investigation sites when the investigational site has been declared ready for the study.

It is expected that eCRF will be completed within 15 days from the performed visit or as soon as source documents are available, except for Serious Adverse Events that require immediate reporting (see Table 3) and for Protocol Deviation requiring pre-approval. A delayed completion of the eCRF will not be considered a Protocol Deviation.

Sponsor study personnel will review all collected data and create data queries for missing data that impacts data analysis. Queries will be sent to the investigator or appropriate support staff for resolution.

Data reported on the eCRFs that are derived from source documents must be consistent with the source documents. Where copies of the original source document as well as print outs of original electronic source documents are retained, these shall be signed and dated by a member of the investigation site team with a statement that it is a true reproduction of the original source document.

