13.2. Data Analysis

A detailed description of the statistical methods will be contained in the Statistical Analysis Plan (SAP). Any change to the data analysis methods described in this section and/or the SAP will require an amendment only if it changes a principal feature of the study description. Any other changes to the data analysis methods will be described and justified in the Final Report or publication.

Based on the clinical practice in the opioid used and number of subjects enrolled per centre/country, an investigation of centre/country effect will be investigated including an independent variable for centres/country in the model as well as summary statistics if needed.

The choice of the imputation method for missing data will depend on the pattern of the missingdata and the type of the imputed variable.

The primary analysis will be performed on all subjects enrolled in the study and monitored with the Capnostream monitor and include all clinical outcomes that occur within the monitoring period(s) as for study design.

It is anticipated that SAS (SAS Institute Inc., Cary, NC, USA) will be used to perform all statistical analyses. Statistical tests will be based on a two-sided significance level of 0.05, and interaction effects will be evaluated at a significance level of 0.10. No adjustments for multiple comparisons will be performed. Additional exploratory analyses will be conducted as deemed appropriate.

The statistics above will be calculated by means of a GEE model as appropriate in order to take into account multiple events per subject and they will be reported together with the interval confidence (IC).

All assumptions for regression models will be assessed by viewing plots of the residual values.

Descriptive statistics will be used to summarize subject characteristics. This will include mean, standard deviation, median, minimum, and maximum for continuous variables, and counts and percentages for categorical variables. To compare subjects with and without the outcome, all categorical variables will be analyzed with the Chi-square test or the Fisher exact test or Cochran-Mantel-Haenszel test for trend for ordinal variables with 3 or more categories, as appropriate. Continuous variable parameter comparisons will be performed using t-test or Wilcoxon test according to the normal or non-normal distribution.

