7.10.2.2 Secondary endpoint#2

The secondary objective#2 will characterize the predictive values of etCO₂, RR, SpO₂ and the IPI⁵ in predicting rORADE. To evaluate the predictive values of the Capnostream monitoring parameters for rORADE, the Sensitivity, Specificity, PPV and NPV will be calculated. rORADE events will be considered the Gold standard and the CS20p monitoring parameters as the measurement to be tested. The population used for this endpoint is PRDPS adjudicated as RD. All Clinical Events occurring during not monitored period will be reported but excluded from the table below. For each RD adjudicated by the CEC, the Capnostream monitoring will be checked if any of the parameter meets at least once the thresholds (RR \leq 6 breaths for \geq 3 minutes, SpO₂ \leq 85% for \geq 3 minutes, EtCO₂ \geq 60 mmHg for \geq 3 minutes or IPI < 3,4,5,6). The table below shows the distribution of the true and false positive and negative for each monitored parameter:

Test		Gold Standard		
Monitoring Parameter		ORADEs/RDs		
RR ≤ 5 breaths for ≥ 3 minutes		YES	NO	Tot
	YES	TP	FP	TP+FP
	NO	FN	TN	FN+TN
	Tot	TP+FN	FP+TN	N
Monitoring Parameter		ORADEs/RDs		
SpO2 ≤ 85% for ≥ 3 minutes		YES	NO	Tot
	YES	TP	FP	TP+FP
	NO	FN	TN	FN+TN
	Tot	TP+FN	FP+TN	N
Monitoring Parameter		ORADEs/RDs		
etCO2 ≤ 15 or ≥ 60 mmHg for ≥ 3 minutes		YES	NO	Tot
	YES	TP	FP	TP+FP
	NO	FN	TN	FN+TN
	Tot	TP+FN	FP+TN	N
Monitoring Parameter		ORADEs/RDs		
IPI <3		YES	NO	Tot
	YES	TP	FP	TP+FP
	NO	FN	TN	FN+TN
	Tot	TP+FN	FP+TN	N
IPI <4		YES	NO	Tot
	YES	TP	FP	TP+FP
	NO	FN	TN	FN+TN
	Tot	TP+FN	FP+TN	N
IPI <5		YES	NO	Tot
	YES	TP	FP	TP+FP
	NO	FN	TN	FN+TN
	Tot	TP+FN	FP+TN	N
IPI <6		YES	NO	Tot
	YES	TP	FP	TP+FP
	NO	FN	TN	FN+TN
	Tot	TP+FN	FP+TN	N
Monitoring Parameter		ORADEs/RDs		
Any Monitoring Parameter RR ≤ 6 breaths for ≥ 3 min or SpO2 ≤ 85% for ≥ 3 min or EtCO2 ≥ 60 mmHg for ≥ 3 min or IPI < 3,4,5,6		YES	NO	Tot
	YES	TP	FP	TP+FP
	NO	FN	TN	FN+TN
	Tot	TP+FN	FP+TN	N

Where:

- N will be all RDs adjudicated by the CEC.
- TP= true positive are all rORADEs and parameter over/below the threshold.
- FN= false negative are all rORADEs but no parameter over/below the threshold.
- FP= false positive are all no rORADE but parameter over/below the threshold.
- TN=true negative are all no ORADEs and no parameter over/below the threshold.

Measure of the accuracy will be:

- Sensitivity: $\{TP/(TP+FN)\}$,
- Specificity: $\{TN/(FP+TN)\}$,
- Positive predictive value: $\{TP/(TP+FP)\}$,

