9.3 Detection Tool

The Detection Tool analyzes each patient's monitoring using an algorithm based on the device episodes thresholds as stated in the primary endpoint. The Detection Tool provides for each patient multiple Episodes. Since there could be multiple episodes in a short time period around each Episode, the Detection Tool is set to aggregate episodes with at most 30 minutes time difference between them in one file. In addition the episodes file consists of time window of 30 min before and after the first and last episode.

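### SAP 7.1.3 keeps patients who never start Capnostream monitoring in the primary analysis set, against Protocol 13.2 and without a stated reason

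*SAP*

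**What the plan says.** SAP 7.1.3 admits to the MFAS eligible, consented patients who "start opioid therapy and monitored in the ward", and assigns the primary analysis to that set. It then adds: "Patients will not be excluded from the MFAS population even if prematurely stops, intermittent use or does not start the monitoring".

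Protocol 13.2 is narrower: "The primary analysis will be performed on all subjects enrolled in the study and monitored with the Capnostream monitor". It also tells the analysis to "include all clinical outcomes that occur within the monitoring period(s) as for study design".

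Four other places bear on what is known about a patient without monitoring:

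- Protocol 9.10: "Capnostream device memory data will be the source for the number and duration of RD episodes".
- SAP 9.3: the Detection Tool analyses each patient's "monitoring using an algorithm based on the device episodes thresholds as stated in the primary endpoint".
- SAP 9.4: clinical events go to the committee first, whether or not a device episode accompanies them.
- SAP 7.10.1.1 and 7.4: the dependent variable is at least one committee-validated RD per patient, and it is not imputed.

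Major protocol deviations remove a patient from the MFAS. The examples in SAP 7.1.2 are a subject who did not "undergo opioid therapy or patient not transferred to the ward"; absent monitoring is not among them. For secondary endpoint 2 the SAP does set a rule: "All Clinical Events occurring during not monitored period will be reported but excluded from the table below".

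On labels, SAP 7.2 and 7.10.1 split only the MFAS into derivation and validation cohorts, and Table 25 is labelled MFAS. Table 26 and Figures 3 to 6 are labelled FAS.

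**The concern.** The protocol and the SAP define different primary populations, and the difference is a group whose outcome is only partly observed. For a patient never connected to the monitor, the etCO₂, respiratory rate, SpO₂ and apnea criteria cannot be assessed. Only the clinical-event route remains. If such a patient has no reported event and is entered as RD-free, the model treats the absence of measurement as the absence of RD.

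Two things are at stake. The observed RD rate, and with it the events per variable on which the sample size rests, would be understated. If never-starting is related to a predictor, that predictor's coefficient and its points would also be distorted.

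**Working it through.** **The plan's own figure.** Protocol 13.1.1: 12 predictors × 10 events per variable = 120 events; 120 / 0.12 = 1000 derivation patients. With 500 for validation, 1500 × 1.10 = 1650. These figures reproduce and are not in dispute.

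**Inputs**

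- True RD rate 12% (Protocol 13.1).
- Share never started, s: not in the documents. Assumed 2% to 15%.
- Detection rate c in never-started patients, through clinical events only: assumed equal to the intervention-based RD rate in Protocol 4.1, 0.3% to 3.4%.
- Never-started patients without an event are coded RD-free.

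**Observed RD rate** = 12% × (1 − s) + c × s

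| s | c = 0.3% | c = 3.4% |
|---|---|---|
| 2% | 11.76 + 0.006 = 11.77% | 11.76 + 0.068 = 11.83% |
| 5% | 11.40 + 0.015 = 11.41% | 11.40 + 0.17 = 11.57% |
| 15% | 10.20 + 0.045 = 10.24% | 10.20 + 0.51 = 10.71% |

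Missed RDs per 1000 patients = 1000 × s × (12% − c). The range runs from 20 × 8.6% = 1.7 to 150 × 11.7% = about 17.5.

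**Effect on a predictor.** Assume RD rates of 18% in carriers and 9.9% in non-carriers. The odds ratio is (0.18/0.82) / (0.099/0.901) = 2.00. The score is 10 × the coefficient, rounded (SAP 7.10.1.1): 10 × ln 2.00 = 6.9, so 7 points. Apply p × (1 − s) + c × s separately in each group:

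| Never started, carriers / non-carriers | Observed OR | 10 × ln OR | Points |
|---|---|---|---|
| 5% / 5% | 1.97–1.99 | 6.8–6.9 | 7 |
| 5% / 2% | 1.92–1.93 | 6.5–6.6 | 7 |
| 15% / 5% | 1.74–1.77 | 5.6–5.7 | 6 |
| 5% / 15% | 2.13–2.23 | 7.6–8.0 | 8 |

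Example, 15% / 5% with c = 0.3%: carriers 0.18 × 0.85 + 0.003 × 0.15 = 0.1535; non-carriers 0.099 × 0.95 + 0.003 × 0.05 = 0.0942; OR = (0.1535/0.8465) / (0.0942/0.9058) = 1.74.

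**What restricting the set removes.** Clinical RDs in never-started patients, per 1000 = 1000 × s × c. At c = 3.4% this is 50 × 0.034 = 1.7 at a 5% share and 150 × 0.034 = 5.1 at 15%, against 120 planned events.

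**Labels.** Only MFAS patients are allocated to a cohort (SAP 7.2, 7.10.1), and the grid in SAP 7.1.3 gives the primary endpoint to the MFAS alone. A patient in the FAS but outside the MFAS belongs to neither cohort, so the five outputs cannot be produced as labelled.

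**The case against.** The case for leaving the text alone has several parts.

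- **Endpoint data are not absent.** The primary endpoint includes respiratory opioid-related adverse events, and clinical events are adjudicated with or without a device episode. This stands. A reader might infer that never-monitored patients have no endpoint data at all, but the documents support only incomplete ascertainment.
- **Monitored in the ward may mean standard-of-care monitoring.** The phrase does not name the Capnostream, and both documents say subjects are monitored per standard of care. This stands as far as it goes: a contradiction inside SAP 7.1.3 is arguable. The conflict with Protocol 13.2, which names the device, is not.
- **A monitoring-period rule exists.** A reader might infer that the primary endpoint has none. Protocol 13.2 supplies one; the SAP does not repeat it.
- **The coding is implied.** At least one RD, without imputation, points to RD-free as the default. That is the natural reading and the one used here. It is also the reading that enters unmeasured patients as non-events.
- **The plan allows changes.** SAP 7.12 permits departures for data availability or low enrollment or event rates, the version history records a population change in 7.1.3, and Protocol 13.2 lets non-principal analysis changes be justified in the final report. None of these gives a reason for this change. Protocol 13.3 does speak of allocating all enrolled subjects, so the protocol is not uniform, but 13.2 is the section that defines the primary analysis population.
- **The group may be small.** Cannula intolerance is an exclusion, and eligibility failures before monitoring exit as screen failures. This stands, and is why the size is called modest.
- **Other repairs would work.** Stating the outcome code, or reporting both sets, would remove the ambiguity. Neither alone would bring the primary set back to the protocol.

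**Conclusion.** The conflict between SAP 7.1.3 and Protocol 13.2 is plain on the text, and confidence in it is high. Confidence in its size is low, because the never-started share and its relation to predictors are assumptions. Over 2% to 15%, the observed RD rate falls from 12% to 11.8% or 10.2–10.7%. A predictor with a true odds ratio of 2.0 shifts by about one point when 15% of one group and 5% of the other never start; at 5% against 2% its points do not change. Severity is minor to should-fix.

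Two stronger inferences are not supported. A reader might conclude from the FAS labels that the validation PPV would be diluted. Patients outside the MFAS are never allocated to a cohort, so no PPV effect follows; the labels are probably left over from the population change in SAP version 2.0. A reader might also suspect bias from unequal monitored time among monitored patients. The documents do not show that hours differ by predictor, and SAP 7.8 already reports monitoring exposure and signal gaps.

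**What to change.** (a) In SAP 7.1.3, strike the clause that retains patients who do not start monitoring, so that the primary set requires Capnostream data as in Protocol 13.2. Keep the provisions for early stopping and intermittent use. State the protocol's monitoring-period limit for the primary outcome in SAP 7.10.1. List clinical events in never-monitored patients separately, as SAP 7.10.2.2 already does for unmonitored periods.

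The cost is one clause, one sentence and one listing. At n = 1000, at most 1.7 of 120 RDs leave the derivation at a 5% share and 5.1 at 15%. The change does not recover the RDs that were never measured: at a 15% share, 850 monitored patients × 12% gives 102 events, or 8.5 per variable. A patient with only minutes of recording also stays in.

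(b) As an editorial correction, relabel Table 26 and Figures 3 to 6 from FAS to MFAS. The cost is five labels.

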7.2 General Methodology

At the end of data collection and according to the number of events per variable and number of patients per site, the data-split or the Bootstrap method will be decided. So, all enrolled patients in the MFAS could be randomly assigned to the Derivation Set (DS) and the Validation Set (VS) at a ratio of 2 to 1 or being used all for the derivation and validation. If the method used will be the data-split the randomization will ensure the two cohorts will be not different and they will be compared in terms of baseline characteristics to check possible confounding covariate.

For FAS and PRDPS descriptive statistics will be used to summarize patient characteristics. This will include mean, standard deviation, median, interquartile range, minimum, and maximum for continuous variables, and counts and percentages for categorical variables. It is anticipated that SAS (SAS Institute Inc., Cary, NC, USA) will be used to perform all statistical analyses. Statistical tests will be based on a two-sided significance level of 0.05, and interaction effects evaluated at a significance level of 0.10. Additional exploratory analyses will be conducted as deemed appropriate.

Table 6 - Characteristics of patients in the Derivation and Validation Cohorts– MFAS (if Data-split)

Table 7 - Characteristics of patients – MFAS (if Bootstrap)

7.3 Center Pooling

Enrollment at any single site will be limited to 330 patients (20%) to limit bias. Based on the clinical practice in the opioid used and number of subjects enrolled per center/country, an investigation of center/country effect will be performed including an independent variable for center/country in the model as well as summary statistics if needed.

7.4 Handling of Missing Data and Dropouts

The choice of the imputation method for missing data will depend on the amount and on the pattern of missingness in the data and the type of the imputed variable. The proc MI procedure will be used to output the missing data patterns for the variables. The outcome variable will not be imputed since the CEC will adjudicate all patients with at least one RD.

7.5 Adjustments for Multiple Comparisons

No adjustments for multiple comparisons or multiple look at data will be performed.

7.6 Derived variables

The statistical evaluations will use some derived variables as listed below. All additional derived variables or changes on the variable listed below are reported in the Statistical Programming Requirements document.

New Variables	Derivation
Monitoring Exposure (minutes)	End monitoring date/time – Start monitoring date/time
Study Exposure (days)	(Study Exit date – date of enrollment)/30.44
BMI35	If BMI >35 then BMI35=1 otherwise BMI35=0
Obese	If BMI >30 then Obese=1 otherwise Obese=0
AGE50	If Age >50 then AGE50=1 otherwise AGE50=0
AGE65	If Age >65 then AGE65=1 otherwise AGE65=0
STOP BANG SCORE	The score is the sum of the following points for each patient: If Snoring loudly= Yes then add 1 point If Tiredness in daytime= Yes then add 1 point If Observed apnea during sleep= Yes then add 1 point If Treated for High blood Pressure= Yes then add 1 point If Body mass index >35 (kg/m2) then add 1 point If Age >50 years then add 1 point If Neck circumference >40 cm (16 inches/17inches according to gender) then add If Gender = Male then add 1 point
Opioids Tolerant §	The FDA definition will be used: A patient is considered opioid tolerant if for at least 1 week he/she has been receiving one of the following: 
 • 60 mg oral morphine/day • 25 mcg transdermal fentanyl/hour • 30 mg oral oxycodone/day • 60 mg oral hydrocodone/day • 8 mg oral hydromorphone/day • 25 mg oral oxymorphone/day • Equi-analgesic dose of any other opioid The Morphine Milligrams Equivalent will be used.
STOP BANG SCORE Class	If 0≤STOP-BANG score ≤2 then STOP BANG SCORE Class= 1 labeled as “Low risk of OSA” If 3≤STOP-BANG score ≤4 then STOP BANG SCORE Class= 2 labeled as “Intermediate risk of OSA” If 5≤STOP-BANG score ≤8 then STOP BANG SCORE Class= 3 labeled as “High risk of OSA”
High Risk Surgery	If occurred within 24 hours
Known or suspected sleep-disordered breathing§	if “Yes to OSA (from Medical History) + YES to first 4 questions of the Apnea History
PCA or epidural or intrathecal therapy	PCA with route as epidural or intrathecal from CM
Multiple opioid or concurrent CNS/sedating medication	According to the Medication coding *(benzodiazepines, sleep aids, muscle relaxant, etc.)
Opioid dosage	According to the Medication coding * (>30mg oral morphine per day or equivalent)
Major organ failure	According to the coding °
Diabetes	if “Yes to Diabetes type I or II”

New Variables§	Derivation
Chronic heart failure or other significant cardiac disease	if "Yes to CHF (from Medical History) + YES to any of the followings from Medical History: Coronary artery disease, Myocardial infarction, Stroke, Transient ischemic attack (TIA), Mitral valve disease, Aortic valve disease, Aortic aneurysm, Cerebral aneurysm, Peripheral vascular disease, Hypertension.
Smoke (> 20 packs per year)§	if "Yes to Smoke (any usage)"

* WHO Drug Dictionary, Version 2009MAR

° MedDRA dictionary, version 20.0

§ all details or potential changes in derived variable are listed in the Statistical Programming Requirements Document.

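### Read literally, SAP 7.6 codes a missing BMI or STOP-BANG item as risk factor absent, and SAP 7.4 does not say that imputation comes before derivation

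*SAP*

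**What the plan says.** SAP 7.6 defines the obesity indicator as "If BMI >30 then Obese=1 otherwise Obese=0" and the higher BMI threshold as "If BMI >35 then BMI35=1 otherwise BMI35=0". The two age indicators follow the same pattern, for example "If Age >65 then AGE65=1 otherwise AGE65=0". None has a branch for a missing source value.

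STOP-BANG is built by adding points for positive findings, beginning with "If Snoring loudly= Yes then add 1 point". There is no rule for an unanswered item. The classes start at zero ("If 0≤STOP-BANG score ≤2 then STOP BANG SCORE Class= 1", labelled as low risk of sleep apnoea), and there is no class for unknown.

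The missing-data plan in SAP 7.4 leaves the method open: "The choice of the imputation method for missing data will depend on the amount and on the pattern of missingness in the data". It adds that "The proc MI procedure will be used to output the missing data patterns for the variables", without saying whether these are source items or derived variables. Only the outcome is excluded from imputation. Nothing in 7.4 or 7.6 sets the order of imputation and derivation.

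SAP 7.10.1.1 makes 0 the reference category for indicator variables, expects most risk factors to be coded 0/1, and turns each final coefficient into points by multiplying by 10 and rounding. Protocol 13.1.1 lists obesity (BMI above 30) among the 12 candidate predictors.

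**The concern.** An else-branch that assigns 0 catches every value that is not known to exceed the threshold, including a value that was never recorded. Followed as written, the rule gives a definite wrong value for some subjects: an obese subject without a recorded BMI becomes non-obese and joins the comparison group. Once coded, the indicator has no gap, so a pattern display or imputation run on the derived variables would find nothing to report or fill.

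STOP-BANG behaves the same way. Each blank counts as a negative answer, so the total can only be too low, and the low-risk class then mixes subjects assessed as low with subjects who were not fully assessed.

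At stake are the odds ratio and the points for obesity, which feed the primary deliverable, and the description of the cohort's sleep-apnoea risk. The reported amount of missing data would also look smaller than it is.

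**Working it through.** **1. What the rule does.** Apply the obesity rule to BMI 25, 32, missing, 41. The result is 0, 1, 0, 1. The source variable has one missing value and the indicator has none. If 7.4 is applied to BMI first, the gap is visible and can be imputed. If it is applied to the indicator, the gap is gone.

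**2. Inputs.**
- From the documents: RD incidence 12% (SAP 6; the plan's own figure 12 × 10 / 0.12 = 1000 derivation subjects reproduces and is not affected here); points = 10 × coefficient, rounded (SAP 7.10.1.1).
- Assumed, because the documents give none: obesity prevalence π = 35% (range 20 to 50%), true odds ratio 2.0, and the missing fraction m. A single-predictor coefficient stands in for the multivariable one.

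**3. Missing at random.** Let p1 and p0 be the RD risks in obese and non-obese subjects. Solving π·p1 + (1 − π)·p0 = 0.12 with an odds ratio of 2.0 at π = 0.35 gives p1 = 0.1702 and p0 = 0.0930. With a fraction m of obese subjects moved to the 0 group, its risk becomes

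p0* = [(1 − π)·p0 + π·m·p1] / [(1 − π) + π·m],

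and the observed odds ratio is [p1/(1 − p1)] / [p0*/(1 − p0*)]. For m = 10%: p0* = (0.0604 + 0.0060)/0.685 = 0.0969, and 0.2051/0.1073 = 1.91.

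| Missing | Obese coded 0, per 1000 | Odds ratio | 10 × ln(OR) | Points |
|---|---|---|---|---|
| 0% | 0 | 2.00 | 6.93 | 7 |
| 1% | 3.5 | 1.99 | 6.88 | 7 |
| 5% | 17.5 | 1.95 | 6.69 | 7 |
| 10% | 35 | 1.91 | 6.47 | 6 |
| 20% | 70 | 1.84 | 6.07 | 6 |
| 30% | 105 | 1.77 | 5.72 | 6 |

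Over prevalence 20 to 50%, 1 to 5% missing gives 1.92 to 2.00 (7 points throughout), and 20% missing gives 1.73 to 1.92 (5 to 7 points).

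**4. Missingness related to RD.** Suppose BMI is missing in 10% of RD subjects and 5% of the others. Per 1000 subjects at π = 0.35:
- coded 1, RD: 350 × 0.1702 × 0.90 = 53.6
- coded 1, no RD: 350 × 0.8298 × 0.95 = 275.9
- coded 0, RD: 120 − 53.6 = 66.4
- coded 0, no RD: 880 − 275.9 = 604.1

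Odds ratio = (53.6 × 604.1)/(275.9 × 66.4) = 1.77, or 6 points. At prevalence 20% it is 1.83 (6 points) and at 50% it is 1.67 (5 points). With the fractions reversed (5% in RD, 10% in the others) the odds ratio rises to 2.11, so the bias need not be toward the null.

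**5. STOP-BANG.** One positive but unrecorded item turns a true 3 into 2 (intermediate to low) and a true 5 into 4 (high to intermediate). Leaving out age and sex, six items can plausibly be missing. At an assumed 1% or 5% missing per item, independently, 1 − 0.99^6 = 5.9% or 1 − 0.95^6 = 26.5% of subjects have at least one gap.

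**The case against.** The strongest reply is that 7.6 is shorthand rather than code. Nothing in 7.4 confines it to derived variables; the source items keep their gaps in the database; and 7.4 permits imputing them first, in which case the problem does not arise. SAP 7.6 also refers additional variables and changes to the Statistical Programming Requirements document, which is not available here and could hold a missing-value rule. SAP 7.10.1.1 lets predictors enter on a continuous scale, where a missing BMI stays missing. Protocol 9.10 and SAP 8 provide for queries on missing or incomplete data.

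Much of this stands. A reader might infer that these gaps can never reach the missing-data plan, or that the SAP imputes absence of risk for every gap. The documents do not support that, because they leave the order of steps open. It does not remove the point, however: 7.6 states an explicit rule, no sentence in the SAP overrides it, the continuous scale is optional, and queries cannot recover a measurement that was not taken.

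Two named variables matter less than they seem to. Adult age is an inclusion criterion (Protocol 8.3), so a missing age is unlikely. STOP-BANG is not itself among the 12 listed predictors; sleep-disordered breathing is, and 7.6 derives it separately. Misclassified STOP-BANG therefore affects description, and the score only if it is used as a predictor.

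**Conclusion.** The point holds as a defect in the stated rule combined with an unstated order of operations. Followed as written, 7.6 turns a missing BMI or STOP-BANG item into an absent risk factor, and this goes unseen if 7.4 is applied to the derived variables.

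Under the assumptions above, the effect on the obesity points is negligible with 5% or less missing at random, modest at 10 to 30% (one point of seven at 35% prevalence), and larger when missingness depends on RD (5 to 6 points instead of 7 at 10% against 5% missing). A reader might also infer that the bias always runs downward, or that gaps concentrate in sicker or urgent patients. The first is true of an individual's apparent risk but not of the odds ratio when missingness is commoner in subjects without RD. The second has no basis in the documents, which say nothing about who lacks these items. The planned sample size is untouched.

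**What to change.** - **SAP 7.6, indicators:** set each derived 0/1 variable to missing when its source value is missing.
- **SAP 7.6, STOP-BANG:** set the total and the class to missing when any item is missing, except that the class is kept when the answered items already determine it. For example, five positive answers place a subject in the high class whatever the blanks hold.
- **SAP 7.4:** state that missing-pattern review and imputation are carried out on the source items, and that the indicators and STOP-BANG are derived afterwards from the completed values. Report the number missing for each item.
- **Statistical Programming Requirements document:** bring it into line, so that no separate missing-value rule conflicts with the SAP.

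The cost is a few sentences in the SAP and the order of two programming steps. No further data are needed, and the sample size does not change.
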